#### 6.7.4. Laboratory Evaluations

Data for the following hematology, serum chemistry, and urinalysis analytes received from central laboratory are to be measured at the scheduled visits in the study flowchart.

**Table 2. Laboratory Tests**

Hematology Test (SI unit)	Serum Chemistry Test (SI unit)	Urinalysis (dipstick)

 
• Red Blood Cell (RBC) Count (<math>10^{12}/L</math>)
 
• Hemoglobin (g/L)
 
• Hematocrit (%)
 
• White Blood Cell (WBC) Count (<math>10^9/L</math>)
 
• Differential WBC (<math>10^9/L</math> and %) 
 
◦ Neutrophils
 
◦ Lymphocytes
 
◦ Eosinophils
 
◦ Basophils
 
◦ Monocytes
 
 
 
• Platelet count (<math>10^9/L</math>)
 
• Mean corpuscular volume (MCV)
 
• Mean corpuscular hemoglobin (MCH)
 
• Mean corpuscular hemoglobin concentration (MCHC)
 
• Red cell distribution width (RDW)
 
	
 
• Alanine aminotransferase (ALT) (U/L)
 
• Aspartate aminotransferase (AST) (U/L)
 
• Total Bilirubin (mmol/L) 
 
◦ Direct Bilirubin*
 
◦ Indirect Bilirubin*
 
 
 
• Total Cholesterol (mmol/L)
 
• Triglycerides (mmol/L)
 
• Alkaline phosphatase (U/L)
 
• Albumin (g/L)
 
• Glucose (mmol/L)
 
• Creatinine (mmol/L)
 
• Creatinine Clearance (mL/m)
 
• Blood Urea Nitrogen (mmol/L)
 
• Calcium (mmol/L)
 
• Potassium (mmol/L)
 
• Sodium (mmol/L)
 
• Uric acid (mmol/L)
 
• Chloride
 
• Bicarbonate
 
 
Coagulation profile Activated Partial Thromboplastin Time (aPTT) Prothrombin Time (PT) / Prothrombin International Normalized Ratio (INR)
	
 
• Specific Gravity
 
• Proteins
 
• Glucose
 
• White Blood Cell Count
 
• Red blood Cell Count
 

\*if Total Bilirubin >2x upper limit of normal (ULN)

If the total bilirubin concentration is  $>2$ x the ULN, direct and indirect reacting bilirubin will be differentiated.

For the purposes of this study, creatinine clearance (CrCl) will be estimated by the Cockcroft-Gault equation as follows:  $CrCl\text{ (ml/min)} = (140 - \text{age}) \times \text{weight (kg)} / (72 \times \text{serum Creatinine (mg/dL)}) \times 0.85$  (*if female*).

Samples for standard aPTT as well as PT/INR will be collected at the visits noted in the assessment schedule.

In accordance with the baseline value definition in Section 5.1.2, the absolute change from baseline will be derived as follows:

Absolute change (unit) = (post-baseline value – baseline value).

All laboratory data will be reported in SI units. All quantitative laboratory test values at each assessed visit will be compared with the relevant reference range in SI units and categorized as:

- Low: Below the lower limit of the reference range.
- Normal: Within the reference range (upper and lower limits included).
- High: Above the upper limit of the reference range.

For analysis purposes, values preceded by a “<” (i.e. those below the limits of quantification) will be considered as half of the value between the lower limit of quantification and 0; values preceded by a “>” sign (i.e. those below or above the limits of quantification) will be considered equal to the upper limit of quantification.

Laboratory data will be summarized by default descriptive summary statistics for continuous and categorical variables for the On-Treatment Analysis Set by treatment group and overall as follows:

- Observed values and change from baseline at each assessed visit for each standard continuous laboratory parameter;
- Number and percentage of patients with categorized (low, normal and high) values at each visit for hematology and serum chemistry;
- Number and percentage of patients with categorized (low, normal and high) values shift relative to the reference range at baseline compared to each post-baseline visit for the following laboratory evaluations: hemoglobin, hematocrit, total bilirubin,

alkaline phosphatase, aspartate aminotransferase (AST), alanine aminotransferase (ALT), and creatinine;

Listings of all clinical laboratory data including derived change from baseline will be provided for the On-Treatment Analysis Set. Within each listing, laboratory values outside the normal ranges will be flagged as either high or low. Box plots of laboratory parameters over time will be presented.

#### **6.7.5. Vital Signs**

The analyses described below will be conducted for the following vital signs assessments respectively:

- systolic blood pressure (mmHg);
- diastolic blood pressure (mmHg);
- pulse rate (beats/min [bpm]);
- body temperature (°C).

In accordance with the baseline value definition in Section [5.1.2](#), the absolute change from baseline will be derived as follows:

Absolute change (unit) = (post-baseline value – baseline value)

Vital sign values will be considered as potentially clinical important (PCI) if they meet criteria listed in [Table 3](#).

**Table 3. Criteria for Potentially Clinically Important Vital Signs Parameters**

Vital Sign	Criteria for observed value	Flag
Pulse Rate	<44 bpm	Low (L)
	≥44 and <100 bpm	Normal
	≥100 and <120 bpm	High (H)
	≥120 bpm	Very High (VH)
Systolic Blood Pressure (SBP)	<90 mmHg	Low (L)
	≥90 and <140 mmHg	Normal
	≥140 and <170 mmHg	High (H)
	≥170 mmHg	Very High (VH)
Diastolic Blood Pressure (DBP)	<50 mmHg	Low (L)
	≥50 and <90 mmHg	Normal
	≥90 and <110 mmHg	High (H)
	≥110 mmHg	Very High (VH)

The following will be summarized by treatment group and overall for the On-Treatment Analysis Set:

- Observed values and change from baseline at each assessed visit for each standard vital sign parameter using default summary statistics for continuous variables;
- Number and percentage of patients with PCI values at each assessed visit for vital sign parameters listed in [Table 2](#);
- Shifts tables from baseline based on the PCI Criteria categories to each post-baseline visit for vital sign parameters listed in [Table 2](#);

A listing of all vital signs data including derived absolute change from baseline will be provided for the On-Treatment Analysis Set.

#### 6.7.6. Electrocardiograms

The following electrocardiogram (ECG) assessments will be taken during the study:

- Heart rate (beats/min);
- Heart-rhythm (sinus, atrial fibrillation, other);

ECG parameters values will be considered PCI if they meet or exceed the upper limit values listed in [Table 4](#).

**Table 4. Criteria for Potentially Clinically Important ECG Values**

ECG parameter (unit)	Criteria	
	Observed value	Change from baseline
Heart rate (beats/min)	≥ 100	Increase of ≥ 15
	≤ 40	Decrease of ≥ 15

The ECG findings will be summarized by treatment group and overall for the On-Treatment Analysis Set as follows:

- Observed values and change from baseline at each assessed visit for each ECG parameter using default summary statistics for continuous variables;
- The number and percentage of patients at each assessed visit for each ECG parameter using default summary statistics for categorical variables;
- The number and percentage of patients with post-baseline PCI values at each post-baseline visit;

A listing of all ECG data including derived change from baseline will be provided for the On-Treatment Analysis Set.

#### **6.7.7. Physical Examination**

Abnormalities identified from physical examination are recorded in the eCRF as Medical History or AEs as appropriate and will be listed and summarized as such [See Sections [6.4.3](#) (Medical History) and [6.7.3](#) (Adverse Events)].

#### **6.7.8. Injection Site Reactions**

All injection site reaction data will be listed by treatment group, patient, and visit/time for the On-Treatment Analysis Set.

#### **6.7.9. Interim Analysis and Data Monitoring**

While the independent Data Monitoring Committee will review accumulating data on a regular basis and will have access to unblinded data, no formal interim analysis will be performed for this study.

### **6.8. Pharmacokinetic/Pharmacodynamic Assessments**

A listing of PK blood sample collection times and Plasma concentrations will be presented for detail analyte(s) from protocol separately for all patients for the Pharmacokinetics Analysis Set.

Pharmacokinetic concentrations will be summarized for the Pharmacokinetics Analysis Set for each timepoint by treatment group and overall using protocol scheduled times and appropriate summary statistics.

See Section [5.2.4](#) for the handling of Plasma concentrations that are BLQ.

### **6.8.1. Pharmacokinetic/Pharmacodynamic Analysis**

Plasma total abelacimab concentration data will be listed by dose, patient, and visit/sampling time point. Descriptive summary statistics will be provided by dose and visit/sampling time point, including the frequency (n, %) of concentrations below the lower limit of quantification and reported as zero.

All pharmacodynamic endpoints will be summarized by visit and treatment group.

Further details of PKPD analyses will be provided in a separate SAP.

### **6.9. Immunogenicity**

Immunogenicity results will be summarized by treatment group and overall for each scheduled collection visit. Standard descriptive statistics will be presented for the observed values. Immunogenicity results will be listed for each patient by treatment group for each scheduled collection visit.

### **6.10. Exploratory Biomarkers**

## **7. Changes in the Conduct of the Study or Planned Analysis**

There were no changes in the conduct of the study at the time of preparing this SAP.

There were no changes in the analysis planned in the protocol of the study at the time of preparing this SAP.

## 8. Appendices

### Appendix 1: Document History

[REDACTED]	[REDACTED]

## 1. INTRODUCTION TO CHANGE DOCUMENTATION

Post database lock change on the statistical analysis plan is documented here.

This document was prepared following final database lock 08Mar2024, final SAP Version 2.0 dated 24Jul2023, and SAP addendum Version 1.0 dated 27Mar2024. The post database lock changes can be found in this document in sections 2.1-2.7. Version 1.0 updates are in sections 2.1-2.4; version 2.0 updates are in sections 2.5-2.7.

## 2. POST-SAP FINALIZATION CHANGES (POST DATABASE LOCK)

The changed texts in the SAP are shown in bold in sections below.

### 2.1. Change in the EoT date and EoS date in the randomized phase of the study for patients enrolled in the extension in section 3.1 of the SAP

The analysis dates to be used are defined as:

- EoT date = Earliest of a) the last dose+60 days or b) the EoT visit **-1 day** or c) death date or d) withdraw consent date or e) EoS visit date
- EoS date = Earliest of a) EoS visit or b) death date or c) withdraw consent date or d) lost to follow-up date; if no EoS date available, then impute EoT visit date **-1 day**

**As per the protocol version 5.0, EoT visit and Extension Day 1 will occur on same day.** In the event that there is an open-label extension period in which the patient enrolls, the following analysis dates to be used are defined as:

- EoT date = **Earlier of a) the last dose+60 days or b) the EoT visit -1 day**
- EoS date = **the EoT visit -1 day**
- EoE date = Earliest of a) the last dose+60 days or b) the EoE visit or c) death date
- EoS extension date = EoS visit; if no EOS visit date available, then impute EoE date

### 2.2. Change in the last dose dates in section 5.1.1 of the SAP

The date of the last dose of treatment for each patient will be taken from the eCRF page. For subjects receiving abelacimab, the last dose is latest Date of injection from the Study Drug SC Administration eCRF page (**before the extension day 1 for patients who enroll in the extension**).

For subjects receiving rivaroxaban, the last dose will come from the following sources, depending on the patient status:

- For those who permanently discontinue treatment, the last dose will be the permanent discontinuation date.
- For those who died but did not permanently discontinue treatment before death, the last dose will be the death date.
- For all other subjects who completed the treatment per the EoT visit page, the last dose will be the EoT visit date **-1 day**.
- If the last dose date is still missing, the last dose will be the last date pills were returned from the Study Drug PO Accountability page.

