#### 6.6 Permanent study drug discontinuation

Permanent study drug discontinuation (PSDD) is allowed at the Investigator's discretion or patient's request at any time. The Investigator should call the [REDACTED] in case of potential PSDDs.

If a patient has what is expected to be a permanent discontinuation of study drug, the patient should complete PSDD visit procedures outlined in the Assessment Schedule ([Appendix 3](#)). At the PSDD visit, unless the patient has a contraindication to anticoagulation, Investigators should arrange patients to be transitioned to appropriate SoC anticoagulation therapy minimizing any gap in anticoagulation since patients with AF are at underlying risk of stroke and systemic embolism (see [Section 7.1](#)).

Patients who permanently discontinue study drug will have an EoS visit approximately 30 days after the PSDD visit and then will be contacted periodically, approximately every 12 weeks, by telephone for SAEs and endpoints (see [Section 7.2](#)) until the site has been notified by the SSC that the randomized period of the trial has ended at which point the patient's participation in the study can be considered completed. Sites should not enter the patient as "complete" in the eCRF until the study has been declared complete, unless the patient has withdrawn their consent to be followed by all possible methods (i.e., in person, remotely, via third party) and refuses to permit review of the medical records.

In certain situations, patients who have previously permanently discontinued study drug and had an PSDD Visit can be allowed to resume study drug. The Investigator should contact the [REDACTED] to determine whether or not a patient who completed a PSDD visit can resume

study drug.

Any patient who permanently discontinues study drug and also wishes to withdraw consent for participation in the study must complete the protocol-specific withdrawal of consent procedures (see [Section 7.3](#)). The Investigator should contact the [REDACTED] to discuss cases in which a patient wishes to withdraw before the decision is made and withdrawal procedures are begun. Withdrawal procedures can begin only after discussion and confirmation that the patient's desire to withdraw full consent.

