### **10.1 Analysis sets**

- On-Treatment: will consist of all randomized patients who received at least one dose of study drug. Patients will be considered to be on-treatment if within 60 days of their last dose of study drug up to the EoT visit of the randomized treatment period.
- Intent-to-Treat (ITT): all patients randomized and dosed to be analyzed according to randomized treatment assignment. Events occurring from randomization through EoS of the randomized treatment period will be included in the analysis.
- Per Protocol: All randomized patients with a treatment compliance rate of at least 80% and do not have any major protocol violations as defined in the final SAP.
- On-Treatment Extension: will consist of all patients who received at least one dose of abelacimab in the extension period. Patients will be considered to be on-treatment if within 60 days of their last dose of study drug to the EoE visit of the extension period.

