### 3. Analysis Populations and Dates

#### 3.1. Analysis Dates

The analysis dates to be used are defined as:

- EoT date = Earliest of a) the last dose+60 days or b) the EoT visit or c) death date or d) withdraw consent date or e) EoS visit date
- EoS date = Earliest of a) EoS visit or b) death date or c) withdraw consent date or d) lost to follow-up date; if no EoS date available, then impute EoT visit date

In the event that there is an open-label extension period in which the patient enrolls, the following analysis dates to be used are defined as:

- EoT date = Earliest of a) the last dose+60 days or b) the EoT visit or c) death date
- EoS date = Earliest of a) the last dose+60 days or b) the EoT visit or c) death date
- EoE date = Earliest of a) the last dose+60 days or b) the EoE visit or c) death date
- EoS extension date = EoS visit; if no EOS visit date available, then impute EoE date

In accordance with ICH E3 and E9, the following analysis sets will be used for the analyses.

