## 5. Data Handling

### 5.1. Time Points and Visit Windows

#### 5.1.1. General Definitions

All assessment days will be related to the first day of first dose of treatment.

Day 1 is defined as first dose of treatment. Relative days after Day 1 are calculated as (assessment date – Day 1 date) + 1. Relative days prior to Day 1 are calculated as (assessment date – Day 1 date). The day prior to Day 1 is Day -1. Day 0 is not defined.

The date of the first dose of treatment for each patient will be taken from the electronic case report/record form (eCRF) page. If the date in this eCRF page is missing, alternatively the date of randomization will be used.

The date of the last dose of treatment for each patient will be taken from the eCRF page. For subjects receiving abelacimab, the last dose is latest Date of injection from the Study Drug SC Administration eCRF page.

For subjects receiving rivaroxaban, the last dose will come from the following sources, depending on the patient status:

- For those who permanently discontinue treatment, the last dose will be the permanent discontinuation date.
- For those who died but did not permanently discontinue treatment before death, the last dose will be the death date.
- For all other subjects who completed the treatment per the EoT visit page, the last dose will be the EoT visit date.
- If the last dose date is still missing, the last dose will be the last date pills were returned from the Study Drug PO Accountability page.

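### For patients who resume study drug after a permanent-discontinuation visit and stay out of the extension, the SAP date rules can close the primary window before the resumed treatment and leave the rivaroxaban last dose undefined

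*SAP*

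**What the plan says.** - **Return to drug.** Protocol 6.6 says that in some situations "patients who have previously permanently discontinued study drug and had an PSDD Visit can be allowed to resume study drug", once the investigator has consulted a designated contact.
- **Early EoS visit.** The same section says "Patients who permanently discontinue study drug will have an EoS visit approximately 30 days after the PSDD visit". Telephone contact for SAEs and endpoints then continues about every 12 weeks until the randomized period ends.
- **On-treatment in the protocol.** For the randomized period, Protocol 10.1 says "Patients will be considered to be on-treatment if within 60 days of their last dose of study drug up to the EoT visit". The EoS visit plays no part.
- **On-treatment in the SAP.** SAP 3.1 ends the window at the earliest of last dose plus 60 days, the EoT visit, "c) death date or d) withdraw consent date or e) EoS visit date". Addendum 2.1 moves the EoT-visit term back one day and keeps clause (e).
- **ITT.** The ITT sensitivity analysis (SAP 6.6.2) runs to the EoS date, and clause (a) of that date is the EoS visit.
- **Last dose.** For abelacimab, "the last dose is latest Date of injection from the Study Drug SC Administration eCRF page" (SAP 5.1.1, kept in Addendum 2.2). For rivaroxaban, "For those who permanently discontinue treatment, the last dose will be the permanent discontinuation date". Other rivaroxaban patients who completed treatment get the EoT visit date, less one day under the addendum.
- **Extension patients.** Addendum 2.1 gives them an EoT date with no EoS-visit term. Addendum 2.2 sets their rivaroxaban last dose at the EoT visit less one day.

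Neither the SAP nor the addendum mentions resumption after PSDD.

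**The concern.** The primary analysis is meant to count bleeding on study drug. The date rules treat a PSDD visit, and the EoS visit that follows it, as the end of the story, whereas the protocol provides for patients to return. For such a patient outside the extension, the window may already be shut while study drug is being taken again. A first major or CRNM bleed after that date is collected through the continuing follow-up but falls outside the primary analysis and outside the ITT sensitivity analysis as well.

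Two features make this worth settling. First, the EoS-visit cut-off is an SAP addition that Protocol 10.1 does not contain, although SAP section 7 reports no change from the protocol's planned analysis. Second, the last-dose definitions are built differently in the two arms. Where they govern, whoever derives the dates must choose a reading for the primary endpoint, in a trial that is open-label between abelacimab and rivaroxaban.

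**Working it through.** **1. The planned event count, as a base for sizing.** Inputs (protocol synopsis, SAP 2.3): HR 0.60, two-sided alpha 0.05, power 80%, 166 events in total, allocation 1:1:1. The protocol's own sample-size text reads HR 0.69; I use 0.60, which the synopsis and the SAP share.

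- Schoenfeld events for one pair: (1.960 + 0.842)² × 4 / (ln 0.60)² = 120.3, rounded up to 121.
- Share of all events falling in one pair, with events proportional to 1 : 0.6 : 0.6: 1.6 / 2.2 = 0.727.
- Total: 121 × 2.2 / 1.6 = 166.4, which matches 166. With 166 events the pair holds 120.7, and power is 80.1%.

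**2. The date rules applied to an example patient.** Assumed dates: PSDD visit and rivaroxaban discontinuation on day 300, drug later resumed, EoT visit on day 700, last abelacimab injection on day 670. Outside the extension, the EoT date is min(last dose + 60, EoT visit − 1, EoS visit).

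| Case | Abelacimab | Rivaroxaban, day-300 date kept | Rivaroxaban, classed as completer |
|---|---|---|---|
| A. EoS visit on day 330, no extension | min(730, 699, 330) = 330 | min(360, 699, 330) = 330 | min(759, 699, 330) = 330 |
| B. No early EoS visit; final EoS visit on day 728 | min(730, 699, 728) = 699 | min(360, 699, 728) = 360 | min(759, 699, 728) = 699 |
| C. Patient enters the extension | min(730, 699) = 699 | not applicable | min(759, 699) = 699 |

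In case A, clause (e) binds in both arms, whatever the last-dose rule. In case B the arms differ only if the day-300 date is kept; the difference is then 699 − 360 = 339 days, about 11 months. In case C nothing is lost.

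**3. Whether ITT recovers the events.** In case A the EoS date is also day 330, so a bleed on resumed drug after that day is outside the ITT window too. For extension patients the addendum sets the EoS date at the EoT visit less one day, so they keep the full period.

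**4. Size.** The documents give no count of resumers. Assumptions: 0.5% to 5% of 400 patients per arm resume (2 to 20 patients), each with 0.25 to 1 year of excluded exposure, at 15% per year on rivaroxaban (SAP 2.3) and 0.60 × 15% = 9% per year on abelacimab. Events lost = n × (1 − exp(−rate × years)).

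- Low end: rivaroxaban 2 × (1 − exp(−0.0375)) = 0.07; each abelacimab arm 2 × (1 − exp(−0.0225)) = 0.04.
- High end: rivaroxaban 20 × (1 − exp(−0.15)) = 2.8; each abelacimab arm 20 × (1 − exp(−0.09)) = 1.7.
- High-end power: 120.7 − 2.8 − 1.7 = 116.2 events in the pair, giving 78.6% against 80.1%. At the low end power stays at 80.1%.

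Using the 1,287 patients actually randomized in place of 1,200 raises the event losses by a factor of 1,287 / 1,200 = 1.07.

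**The case against.** The strongest reply is that the SAP nowhere says an earlier discontinuation date governs a rivaroxaban patient who returned to drug. The protocol glossary and section 7.2 define discontinuation as stopping for good before the planned end, and section 6.6 triggers the PSDD visit on an expectation only. On that reading, a resumer still on tablets at the end is a completer, and one who stops again carries a later date. This stands: the rivaroxaban rule is undefined for these patients. It does not remove the problem. The completer rule is a residual class after those who permanently discontinue, so a patient with a recorded PSDD can as easily be placed in the first group. Nor does it touch clause (e), which is a stated rule and closes the window under either classification.

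Other points also stand. Extension patients are protected. Protocol 6.5 allows temporary interruption without limit, so an expected return need not involve a PSDD visit at all. A patient whose PSDD followed a primary bleed already has a first event. These points keep the affected group small, but they do not empty it, because the extension is optional for sites and for patients.

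A last objection is that running the window to the final course counts the off-drug gap as on-treatment. That is true: stopping at month 6 and resuming at month 15 adds about 9 − 2 = 7 months beyond the 60-day limit. The abelacimab latest-injection rule already does this where it governs.

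**Conclusion.** The point holds in a limited form. For resumers who do not enter the extension, an EoS visit held after PSDD can close the primary window, and the ITT window, before the resumed treatment. It does so alike in both arms and against Protocol 10.1. Where no early EoS visit was held, the last-dose rules may treat the arms differently, depending on a choice that the SAP leaves open.

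A reader might infer more: that the SAP drops bleeds on resumed rivaroxaban while keeping those on resumed abelacimab, and so tilts the comparison. The documents do not support that. Divergence needs a resumption, no early EoS visit, and use of the first discontinuation date, and the SAP does not prescribe the last of these. Person-time is also censored together with the events, so the consequence is lost information and possible informative censoring, with no direction shown.

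Under the assumed range (0.5% to 5% resuming, 0.25 to 1 year each, all of it excluded), the loss is at most about 2.8 rivaroxaban events and 1.7 per abelacimab arm, or 1.5 percentage points of power. It is likely small unless resumption was common, and only a count of resumers can settle that.

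**What to change.** - **Last dose (SAP 5.1.1, Addendum 2.2).** In both arms, define it as the last dose of the patient's final course of randomized treatment, so that a PSDD followed by resumption does not set it.
- **Analysis dates (SAP 3.1, Addendum 2.1).** Let clause (e) of the EoT date and clause (a) of the EoS date use only an EoS visit held after that final course.
- **Listing.** List resumers by arm, with PSDD, resumption, EoS-visit and last-dose dates.
- **Status.** The database was locked on 08Mar2024, so put this in a further addendum and report it as a sensitivity analysis beside the primary result. Include a variant that excludes off-drug time more than 60 days after the last dose before resumption.

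The cost is a few sentences and a small derivation change, largely using dates that the SAP already takes from the eCRF. The downside is that, without the variant, some off-drug gap time counts as on-treatment in both arms, as the abelacimab rule already allows. If the listing shows no resumers outside the extension, a sentence saying so is enough.
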